19.4. APPENDIX 4: MONTHLY QUESTIONNAIRE

Introduction: Please take a moment to complete the following questionnaire relating to your child's wheezing condition. The questions will help us identify wheezing exacerbations and assess your child's quality of life.

Question 1: Did your child experience any wheezing symptoms during the last month?

Not at all	Once or twice	Once every week	2 or 3 times a week	4 or more times a week
				

Question 2: Was the child unable to go to childcare because of breathing problems?

Yes	No	N/A
		

If **yes**, please state how many days: _____ (Number)

Question 3: Did you have to take your child for an emergency appointment with your GP, urgent care or hospital because of wheezing?

Not at all	Once or twice	Once every week	2 or 3 times a week	4 or more times a week
				

Question 4: Was your child treated with inhaled or oral corticosteroids?

Yes	No
	

If **yes**, what was the dose, frequency and duration?

Dose:	Frequency:	Duration:
_____	_____	_____

Question 5: Was your child given β 2 agonists (blue inhaler, rescue therapy)?

Yes	No
	

If **yes**, what was the dose, frequency and duration?

Dose:	Frequency:	Duration:
_____	_____	_____

Question 6: Did you have to take days off work because your child had wheezing or breathing difficulties?

Yes	No
	

If **yes**, how many days did you take? Specify number: _____ (days)

Survey's ending message: "We thank you for your time spent taking this survey. Your response has been recorded."

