7.2. INCLUSION AND EXCLUSION CRITERIA

7.2.1. CHILDREN

INCLUSION CRITERIA	EXCLUSION CRITERIA

1. Patients aged one to five years old presenting to primary care or to the emergency department or to secondary care (e.g., outpatients) or identified from primary care records and have been diagnosed with wheezing by their GP or paediatrician who has decided to prescribe any bronchodilator, ICS or montelukast on clinical grounds
	
1. Inability to understand and cooperate with study procedures
 
2. Significant co-morbidity (respiratory or otherwise), for example cystic fibrosis (excluding atopic disorders such as eczema, allergic rhinitis and food allergy)
 
3. Withholding or withdrawal of informed consent

2. Parents/Carers able to understand and familiarize themselves with the study and are willing to provide informed consent
	
4. Severe procedural anxiety (needle phobia)
 
5. Child is already enrolled in another study involving investigational medicinal product (CTIMP)
 
6. History of near-fatal asthma that resulted in intubation / assisted ventilation.

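### Question 4 of the monthly form merges inhaled and oral steroids and asks no reason, so the oral-steroid outcome cannot be cleanly tied to wheeze

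*Combined protocol and SAP*

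**What the plan says.** Appendix 4 is the form that parents complete each month. Its introduction opens "Please take a moment to complete the following questionnaire relating to your" and goes on to name the child's wheezing condition. The items then attribute events in different ways:

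- Visits (source of the primary outcome): "Question 3: Did you have to take your child for an emergency appointment with your GP, urgent care or hospital because of wheezing".
- Childcare days: "Question 2: Was the child unable to go to childcare because of breathing problems".
- Carer work days: "Question 6: Did you have to take days off work because your child had wheezing or breathing difficulties".
- Steroids: "Question 4: Was your child treated with inhaled or oral corticosteroids". This has a single Yes/No and a single set of dose, frequency and duration fields. Neither a reason nor a number of courses is requested.

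Section 6.1 ties only the primary outcome to wheeze. It lists childcare days, carer days off work and oral steroid use with no cause, and it restricts the steroid outcome to the oral route. Sections 6 and 9 and Appendix 2 describe the monthly form as capturing oral steroid use with dosage; they do not mention inhaled steroids there. Section 11 has no rule for separating routes or attributing courses.

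**The concern.** The study asks whether three markers predict wheezing exacerbations, and the form states its purpose in the same terms: "The questions will help us identify wheezing exacerbations and assess your" child's quality of life. An oral steroid course is a natural companion to the visit count, but only if it can be identified as oral and linked to a respiratory episode. Question 4 allows neither with confidence.

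Two things are at stake. First, children can enter on an inhaled steroid prescription (section 7.2.1), so a Yes may mean only that regular inhaled treatment continued. Second, an oral course for a non-respiratory illness would count alongside one for wheeze. If such courses are unrelated to the markers, they shrink the contrast between marker groups. If they are more frequent in one marker group, they can create or hide a contrast. Section 4.3 says the pilot data are to inform the power calculations of a later trial, and a mixed answer cannot be separated reliably afterwards.

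**Working it through.** **Inputs from the documents.** The item wordings above; a recruitment target of 100 (section 5); a 0.05 significance level with sidedness not stated, and chi-squared, Fisher, t and Mann-Whitney tests (section 11). There is no event rate, effect size, power or sample-size derivation, so there is no figure to reproduce.

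**Step 1: can the oral outcome be rebuilt from Question 4?** A month with inhaled treatment only, with an oral course only, or with both gives the same Yes. The free-text dose may reveal the route when one product was used. When both were used, one set of fields must hold two treatments. The reason is never recorded. TRACK item 5 (Appendix 3) does name oral steroids alone, but on a graded scale over 12 months, with no course count and no reason.

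**Step 2: what might unrelated oral courses do?** Everything here is assumed. Let p be the probability over 12 months of at least one wheeze-related oral course and q that of at least one unrelated course, independent of it. The recorded probability is p' = 1 - (1 - p)(1 - q). With equal q in both groups the difference becomes (p1 - p0)(1 - q). Take p0 = 0.30 (marker-negative) and p1 = 0.60 (marker-positive), N = 100, two-sided 0.05, normal approximation for two proportions. The 30/70 split means 30 marker-positive and 70 marker-negative.

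| q | negative | positive | difference | ratio | power, 50/50 | power, 30/70 |
|---|---|---|---|---|---|---|
| 0 | 0.30 | 0.60 | 0.30 | 2.00 | 87% | 81% |
| 0.10 | 0.37 | 0.64 | 0.27 | 1.73 | 78% | 71% |
| 0.20 | 0.44 | 0.68 | 0.24 | 1.55 | 68% | 60% |
| 0.40 | 0.58 | 0.76 | 0.18 | 1.31 | 48% | 40% |

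For q = 0.20: 1 - 0.70 × 0.80 = 0.44 and 1 - 0.40 × 0.80 = 0.68. With a small background, q = 0.05, the values are 0.335 and 0.62, ratio 1.85. With p of 0.30 against 0.50 and a 50/50 split, power is 53%, 44%, 36% and 24% at the four values of q in the table.

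**Step 3: unequal background, no true difference.** Take p = 0.40 in both groups and a 50/50 split.

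- q of 0.20 (positive) against 0.10 (negative): 1 - 0.60 × 0.80 = 0.52 against 1 - 0.60 × 0.90 = 0.46, ratio 1.13, about 9% rejection in that direction.
- q of 0.30 against 0.10: 0.58 against 0.46, ratio 1.26, about 22% rejection in that direction.

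Nominal one-direction rejection is 2.5%. Swapping the backgrounds turns the ratios into 0.46/0.52 = 0.88 and 0.46/0.58 = 0.79, so the direction depends on a figure that the documents do not give.

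**Step 4: childcare and work days.** For assumed mean days of 2 and 4, adding 0.5, 1 or 2 background days to both groups gives ratios of 4.5/2.5 = 1.80, 5/3 = 1.67 and 6/4 = 1.50. The mean difference stays at 2 days.

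**The case against.** A reader might infer that the form counts childcare and work days for every breathing problem and steroids for every reason, so that the secondary outcomes are diluted or biased. The documents do not support that.

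- The introduction frames every item around the wheezing condition, and nothing shows how parents would answer.
- Section 6.1 gives no cause for these outcomes. Questions 2 and 6 are narrower than what it lists and mismeasure nothing. Their scope is also close to that of the TRACK score, which asks about breathing problems in general.
- Every rate in the illustration is assumed, and equal background days leave a mean difference unchanged.
- Bias along the marker is conjecture. The comorbidity exclusion does keep atopic children in ("excluding atopic disorders such as eczema, allergic rhinitis and food allergy"), but eligibility does not show that they receive more unrelated oral courses. Section 2 also excludes a history of anaphylaxis while section 7.2.1 does not, so even the place of allergic reactions is unsettled.
- Wheeze-only wording is no clean remedy, because section 4.1 regards parental recognition of wheeze as unreliable.

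All of this stands, and it removes any claim of demonstrated dilution or bias and any case for redefining absence days as wheeze-only. It does not answer the point on Question 4. The introduction may discourage reporting of unrelated courses, but it does not separate oral from inhaled treatment or record a reason. Review visits or medical notes might supply both, but the plan does not name either as a source for this outcome.

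**Conclusion.** The point holds for Question 4 and is minor. The oral-steroid outcome shares one answer and one set of dose fields with inhaled treatment and carries no indication, so it can include courses for other illness and cannot be cleanly tied to wheeze. The size and direction of any distortion are unknown. The ratios of 1.85 to 1.31 (from 2.00) and of 1.13 to 1.26 (from 1.00) show what assumed backgrounds would do and are not estimates for this study.

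Questions 2 and 6 are a matter of consistency: their wordings differ from each other and from Question 3, but contradict no stated definition. Question 5, on rescue inhalers, also asks no reason. The primary outcome item is tied to wheeze and is unaffected. These are secondary outcomes of a feasibility study, so the case for change rests on low cost and on information that the form as written cannot reliably supply later.

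**What to change.** - **Question 4.** Ask about inhaled and oral treatment separately. For oral treatment, enter the number of courses *for wheezing or breathing problems* and the number *for another reason*, keeping the dose, frequency and duration fields for each route.
- **Section 6.1.** Define the oral-steroid outcome as the respiratory-attributed courses, and report the all-cause total as a sensitivity result.
- **Questions 2 and 6.** Use one wording for both and keep breathing problems as the quantity collected. Optionally add a sub-count, *of which because of wheezing*. A two-way split into wheezing and any other reason should be avoided: the second box would take in non-respiratory causes, and the breathing-problem days now collected could not be recovered.

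The cost is one or two more boxes on an electronic form and a few lines in section 6.1, with no extra visits. The downside is reliance on parental attribution, which the protocol itself calls inaccurate; Question 3 already depends on it, and the all-cause total limits the damage.

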ELIGIBILITY: (children)	Inclusion criteria: 
1. Patients aged one to five years old presenting either to primary care or to the emergency department or to secondary care (e.g., outpatients) or identified from primary care records and have been diagnosed with wheezing by their GP or paediatrician who has decided to prescribe any bronchodilator, ICS or montelukast on clinical grounds2. Parents/Carers able to understand and familiarize themselves with the study and are willing to provide informed consent Exclusion criteria: 
1. Inability to understand and cooperate with study procedures2. Significant co-morbidity (respiratory or otherwise), for example cystic fibrosis (excluding atopic disorders such as eczema, allergic rhinitis and food allergy)3. Withholding or withdrawal of informed consent4. Severe procedural anxiety (needle phobia)5. Child is already enrolled in another study involving investigational medicinal product (CTIMP)6. History of anaphylaxis or near-fatal asthma that resulted in intubation / assisted ventilation.
ELIGIBILITY: (Healthcare professionals)	Inclusion Criteria: 
1. Doctors and nurses working in GP practices. Exclusion Criteria: 
1. Inability to understand and cooperate with study procedures.

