5. STUDY'S AIM AND OBJECTIVES

AIM: To obtain pilot data to test the hypothesis that aeroallergen sensitisation (confirmed by a wheal formation with a diameter ≥ 3 mm after a skin prick test is performed), FeNO (offline method) ≥ 10 ppb and a peripheral blood eosinophil count $\geq 300/\mu\text{l}$, alone or in combination, can predict future wheezing exacerbations in preschool children as well as response to treatment with inhaled corticosteroids, as a preliminary to a large, randomised controlled trial. Also, that these tests are acceptable to families.

OBJECTIVES:

- To recruit 100 preschool children with a history of wheeze, aged one to five years old, and determine atopic status, peripheral blood eosinophil count (point of care test) and FeNO (offline method).
- To evaluate the feasibility and acceptability of these tests
- To categorize the children according to the biomarkers tested and assess whether any or all, alone or in combination, predict future wheezing exacerbations as well as determine the clinical outcome over one year
- To obtain parents' and doctors' insights into whether the biomarkers mentioned above could be used in a future intervention study.

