In addition, we will ask them to fill in a very short electronic questionnaire after the study is finished, to check their perspective and acceptability on these biomarkers being used to guide children's therapy in the future (Appendix 5: Exit Questionnaire).

The whole duration of this study is expected to be 20-21 months, with 1-year follow-up for each patient included.

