6.1. STUDY OUTCOME MEASURES

Primary outcome:

Acute attacks of wheeze defined as requiring an unscheduled health care visit

Secondary outcomes:

- Carer days off work
- Days the child unable to attend childcare facility
- Use of oral corticosteroids
- Use of inhaled β -2 agonist (rescue therapy)
- Assessment if children's respiratory or wheezing condition is under control by using the TRACK™ score questionnaire (Test for Respiratory and Asthma Control in Kids) (Appendix 3).

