9. ASSESSMENT AND FOLLOW-UP

We will arrange for a short monthly electronic questionnaire to be sent by email to the parents/carers, in order to record on a monthly basis, the days their child was out of childcare, days the carer missed from work, unscheduled health care visits and use of rescue therapy or oral corticosteroids (including dosage) (Appendix 4: Monthly Questionnaire). In addition, we will record the children's TRACK™ score (Test for Respiratory and Asthma Control in Kids) (Appendix 3: TRACK™ score questionnaire) every 3 months, to assess wheeze control. There will be review visits every 3 months, to evaluate their progression in person, but if not feasible, video calls will be arranged through Microsoft Teams. In the case of any incidental findings, there will be thorough evaluation of potential benefits or harms before disclosing the information to the child's parent. As this is an observational study, no interventions can be done in the case of incidental findings and parents will be advised to discuss this with their child's GP or paediatrician.

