 20	 15	 10	 5	 0	

2. During the past 4 weeks, how often did your child's breathing problems (wheezing, coughing, shortness of breath) wake him or her up at night?
					
Not at all	Once or twice	Once every week	2 or 3 times a week	4 or more times a week	
 20	 15	 10	 5	 0	

3. During the past 4 weeks, to what extend did your child's breathing problems, such as wheezing, coughing or shortness of breath, interfere with his or her ability to play, go to school or engage in usual activities that a child should be doing at his or her age?
					
Not at all	Slightly	Moderately	Quite a lot	Extremely	
 20	 15	 10	 5	 0	

4. During the past 3 months, how often did your need to treat your child's breathing problems (wheezing, coughing or shortness of breath) with quick relief medications (e.g., albuterol, Ventolin®)
					
Not at all	Once or twice	Once every week	2 or 3 times a week	4 or more times a week	
 20	 15	 10	 5	 0	

5. During the past 12 months, how often did you child need to take oral corticosteroids (e.g., prednisone, prednisolone, Decadron®)
					
Not at all	Slightly	Moderately	Quite a lot	Extremely	
 20	 15	 10	 5	 0	

Total Score

Figure 1. The TRACK™ Score Questionnaire. TRACK (Test for Respiratory and Asthma Control in Kids) is a trademark of AstraZeneca group of companies © 2009. TRACK score less than 80 means that the child's breathing problems are out of control. TRACK score above 80 means that the child's breathing problems seem to be in control.

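### The absence outcome asks only about childcare, so school days lost by the oldest children can be recorded as No or N/A

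*Combined protocol and SAP*

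**What the plan says.** Section 7.2.1 admits "Patients aged one to five years old presenting to primary care or to the emergency department", or to secondary care, or identified from primary care records. The eligibility table in Section 2 gives the same age range. Neither says whether the upper limit is the fifth or the sixth birthday. Section 6 sets the observation period: "with 1-year follow-up for each patient included".

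Section 6.1 lists as a secondary outcome "Days the child unable to attend childcare facility". Section 2 lists the same outcome without the word for days. Section 9 says that the monthly form will record "the days their child was out of childcare, days the carer missed from work, unscheduled health care visits", along with medication use.

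Appendix 4, Question 2, is the item that supplies this outcome: "Was the child unable to go to childcare because of breathing problems". The answers are Yes, No and N/A, and the number of days is requested only after Yes. No section defines childcare as including nursery or school, says when N/A applies, or says how an N/A month enters the analysis. Section 11 is silent on the last point.

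School does appear elsewhere in the study's instruments. Item 3 of the TRACK questionnaire (Appendix 3) asks about the child's "ability to play, go to school or engage in usual activities that a child should be doing".

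**The concern.** The age range and the year of follow-up together take some children to an age at which they may attend school and not childcare. For those children the wording of Question 2 does not match the event of interest. A parent whose child missed four school days through wheeze may answer Yes and enter four, may answer No because the child does not go to childcare, or may tick N/A for the same reason. The three answers give four days, zero days and no count for the same illness.

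The ambiguity affects only children old enough for school, so the error depends on age, and it can begin part-way through a child's follow-up when that child starts school. Section 11 plans unadjusted two-group tests (chi-squared, Fisher, t or Mann-Whitney), so nothing in the analysis would take account of an age-dependent error. Section 4.3 says that pilot data are needed to inform power calculations for a later trial. An absence rate that mixes three readings of one question would be a poor input to such a calculation.

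**Working it through.** The plan gives no figure for this outcome, so there is none to reproduce. The check has two parts.

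**1. Can another item supply the missing days?**

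| Item | Covers school? | Gives the child's days absent? |
|---|---|---|
| Appendix 4, Question 2 | Not named | Yes, but only after a Yes answer |
| Appendix 4, Question 6 (carer days off work) | Indirectly | No; it counts the carer's days and is a separate outcome |
| TRACK item 3 | Named | No; it is a graded score over four weeks, sent every three months |

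No other item can restore the count.

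**2. How much follow-up is exposed?**

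Inputs from the documents: lower entry age 1 year; upper entry limit U, either the fifth birthday (U = 5) or the sixth (U = 6), because the criterion fits both; 12 months of follow-up; 100 children, hence 100 × 12 = 1,200 child-months.

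Assumptions that are not in the documents: entry ages spread evenly from 1 to U; no dropout; school starting at age s, with s between 4 and 5.

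For a child entering at age a, the share of the year spent at or above age s is a + 1 − s, limited to the range 0 to 1. Averaging over entry ages:

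- The share rises from 0 to 1 as a goes from s − 1 to s, which contributes an area of 0.5.
- It equals 1 from s to U, which contributes U − s.
- Mean share = (0.5 + U − s) / (U − 1).
- Proportion of children with any exposed time = (U − s + 1) / (U − 1).

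| Upper limit U | School start s | Share of child-months | Of 1,200 | Children with any |
|---|---|---|---|---|
| 5 | 5.0 | 0.5/4 = 12.5% | 150 | 1/4 = 25% |
| 5 | 4.5 | 1.0/4 = 25% | 300 | 1.5/4 = 37.5% |
| 5 | 4.0 | 1.5/4 = 37.5% | 450 | 2/4 = 50% |
| 6 | 5.0 | 1.5/5 = 30% | 360 | 2/5 = 40% |
| 6 | 4.5 | 2.0/5 = 40% | 480 | 2.5/5 = 50% |
| 6 | 4.0 | 2.5/5 = 50% | 600 | 3/5 = 60% |

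The share is above zero in every combination. It counts months in which the question could be misread. It does not count months that were misread or days that were lost.

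**The case against.** Several objections carry weight.

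- **Parents may read childcare broadly.** Some will count a school day as a childcare day, and for them nothing is lost. This stands: the loss is possible, not certain. But the form gives no guidance, and different readings by different parents are themselves measurement error.
- **The population is called preschool throughout.** This makes the sixth-birthday figures less plausible. It does not remove the problem, because a child who enters shortly before the fifth birthday can start school during the year.
- **The consequence is limited.** This is one of five secondary outcomes in a 100-child feasibility study. The primary outcome, unscheduled visits, does not depend on Question 2. The three-monthly review contacts also offer a chance to clarify answers, although the protocol does not ask for this.

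A reader might go further and infer that the outcome is under-recorded mainly in biomarker-positive children, which would pull the comparison towards no difference, because Section 4.1 describes more airway inflammation in older children. The documents do not support that. Section 4.1 sets children at about one year beside children at 30 months, from separate studies, and describes airway findings. It does not report skin prick, exhaled nitric oxide or finger-prick eosinophil positivity at ages four to five. The direction would also depend on which group loses more days and on whether the lost days are scored as zero. An N/A month is not a zero: if treated as missing, it loses information and does not lower the count.

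**Conclusion.** The point holds as a measurement weakness in one secondary outcome. As written, the form lets school absence be counted, zeroed or left blank according to the parent's reading of one word, and this affects only children old enough to attend school. Under the stated assumptions, 12.5% to 37.5% of child-months are exposed if entry ends at the fifth birthday, and 30% to 50% if it ends at the sixth. The range is wide because the documents give neither an entry-age distribution nor a school-starting age.

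These percentages should not be read as the proportion of absence days missed, which cannot be derived from the documents. Nor can the size or direction of any bias between biomarker groups. The undefined upper birthday matters here only because it widens the range; it is a separate gap in detail.

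**What to change.** Reword Question 2 in Appendix 4, and the matching outcome in Sections 2 and 6.1, to cover childcare, nursery or school. Make the same change where Sections 2, 6, 7.1 and 9 and Appendix 2 describe the monthly form. State on the form that N/A is only for a child who attends none of these. State in Section 11 that days lost are calculated over months in which the child attends at least one of them, so that N/A months leave the denominator and are not scored as zero.

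The cost is a minor amendment to an electronic form and a few lines of protocol text. Ethics approval is already in place (Section 12.1) and departures from the protocol need sponsor and HRA review (Section 17), so it should go through that route. Parents have no extra question to answer. One limitation remains: neither the present nor the reworded form records how many days a week a child attends, so part-time childcare and full-time school would still be pooled with different opportunity for absence.

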19.2. APPENDIX 2: FOLLOW-UP PLAN

We will arrange for a short monthly electronic questionnaire to be sent by email to the parents/carers, in order to record on a monthly basis, the days their child was out of childcare, days the carer missed from work, unscheduled health care visits and use of rescue therapy or oral corticosteroids (including dosage) (Appendix 4: Monthly Questionnaire). In addition, we will record the children's TRACK™ score (Test for Respiratory and Asthma Control in Kids) (Appendix 3: TRACK™ score questionnaire) every 3 months, to assess wheeze control. The questionnaires will be made and sent through the Qualtrics® questionnaire platform (offered by Imperial College London), which allows data gathering data according to the GCP guidelines and as used for years in the Breathing Together study (19). Additionally, the questionnaire form submission will not collect parents' IP address or geolocation. There will also be review visits every 3 months, to evaluate their progression in person, but if not feasible, video calls will be arranged through Microsoft Teams.

	Months											
	1	2	3	4	5	6	7	8	9	10	11	12
Primary Care Visit		X			X			X				X
Video Call (Microsoft Teams) ¹		X			X			X				X
Biomarker Testing ²			X ³									
TRACK™ Score Questionnaire ⁴			X			X			X			X
Monthly Questionnaire	X	X	X	X	X	X	X	X	X	X	X	X
Focus Group												X

Table 2. The follow-up plan after preschool wheezers' recruitment.

¹ In case they are not available for primary care visit

² Testing the 3 biomarkers, blood eosinophils, atopic sensitisation and FeNO (offline method).

³ A second testing will be performed 3 months after the first one and will be **optional**. Parents will be informed through the patient information sheet, as well as in person that they have the option to deny participation of their child in this second testing. It is written in the informed consent form as well.

⁴ The TRACK™ score will be sent to the parents/carers by email or SMS every 3 months and will be incorporated to the monthly questionnaire. They will be sent through the Qualtrics® questionnaire platform.

19.3. APPENDIX 3: TRACK™ SCORE QUESTIONNAIRE (TEST FOR RESPIRATORY AND ASTHMA CONTROL IN KIDS)

1. During the past 4 weeks, how often was your child bothered by breathing problems, such as wheezing, coughing or shortness of breath?
					
Not at all	Once or twice	Once every week	2 or 3 times a week	4 or more times a week	

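### The monthly form takes emergency visits only in frequency bands and pools oral with inhaled steroids, so attack counts and oral courses cannot be reliably derived

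*Combined protocol and SAP*

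**What the plan says.** Section 6.1 defines the primary outcome as "Acute attacks of wheeze defined as requiring an unscheduled health care visit" and lists "Use of oral corticosteroids" as a secondary outcome in its own right. It does not say whether attacks are analysed as a count, a rate or any versus none.

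The study summary, sections 6, 7.1 and 9, and Appendix 2 all name the monthly form as the record. In Appendix 2 it is to capture "unscheduled health care visits and use of rescue therapy or oral corticosteroids (including dosage) (Appendix 4: Monthly Questionnaire". The form tells parents that "The questions will help us identify wheezing exacerbations".

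The two items concerned, both in Appendix 4, are:

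- "Question 3: Did you have to take your child for an emergency appointment with your GP, urgent care or hospital because of wheezing". The answer is one of five boxes: none, one or two, weekly, two to three a week, four or more a week. There is no number, no date and no recall period in the item.
- "Question 4: Was your child treated with inhaled or oral corticosteroids". This is one yes/no, followed by one set of dose, frequency and duration fields, with no drug, route or number of courses.

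Questions 2 and 6 on the same form do ask for a number of days. The only item specific to oral steroids is TRACK item 5 in Appendix 3, "During the past 12 months, how often did you child need to take oral corticosteroids", answered on a five-point scale. Appendix 2 says TRACK "will be incorporated to the monthly questionnaire" every three months.

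Section 4.3 wants pilot data for power calculations. Section 11 lists chi-squared, Fisher, t and Mann-Whitney tests without saying which summary of the primary outcome they apply to.

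**The concern.** The form does not collect what the protocol says it records. The visit boxes are the ones used for symptom frequency in Question 1 and in TRACK. They suit symptoms but not emergency visits, where the distinctions that matter are none, one, two and three. Repeat visits for one attack also cannot be told from separate attacks.

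For steroids, an inhaled corticosteroid is one of the qualifying prescriptions in section 7.2.1. Some children will therefore answer yes to Question 4 every month for that reason alone, and one dose line cannot hold both treatments.

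What is at stake is the attack rate and its variation between children. Section 4.3 describes response in the earlier crossover study partly as fewer attacks, so a count is a natural outcome for the later trial, although the documents do not fix one. Any rate taken from this form depends on how the one-or-two box is scored and on which box parents tick after three visits. The plan settles neither.

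**Working it through.** The documents give no event rate, effect size or sample-size calculation, so there is no stated figure to reproduce.

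**1. What the boxes allow.** A child with *k* months in the one-or-two box had between *k* and 2*k* visits in those months: 3 months means 3 to 6, and 6 months means 6 to 12. A weekly tick means about 52/12 = 4.3 visits a month. Exactly three visits fits no box.

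**2. Error in the visit rate.** Assumptions: 2 to 6 visits per child-year, Poisson months, gamma frailty with variance 1. With m = rate/12, P(n visits in a month) = mⁿ/(1+m)ⁿ⁺¹.

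If months of three or more visits were known exactly:

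- one-or-two scored 1: error = -P(2)/m = -m/(1+m)³. At 2 per year, -0.167/1.588 = -10%; at 6 per year, -0.5/3.375 = -15%.
- one-or-two scored 1.5: error = 0.5[P(1) - P(2)]/m = 0.5/(1+m)³. At 2 per year, +31%; at 6 per year, +15%.

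Three-visit months add a further term. If they go in the one-or-two box, it is -2m²/(1+m)⁴ with score 1 (about -3 points at 2 per year, -10 at 6) or -1.5m²/(1+m)⁴ with score 1.5. If they go in the weekly box, scored 4, it is +m²/(1+m)⁴. Scoring 4-6 visits as 4, 7-14 as 10 and 15 or more as 17 moves the results by less than one point.

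**3. Effect on a later trial.** Assumptions: yearly visit counts, negative binomial, rate ratio 0.7, 80% power.

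n per arm = (1.96+0.84)² × (1/μ + 1/(0.7μ) + 2k) / (ln 0.7)²

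Here μ is the yearly rate and k the dispersion. With k = 1, μ = 2 gives 61.6 × 3.214 = 198, and μ = 6 gives 61.6 × 2.405 = 148. Putting in μ and k as estimated from the coded data gives:

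| Three-visit months ticked as | One-or-two scored | Visit-rate error | Coded k | Change in planned n |
|---|---|---|---|---|
| one-or-two | 1 | -14% to -25% | 0.64-0.77 | -14% to -20% |
| one-or-two | 1.5 | +7% to +29% | 0.64-0.82 | -20% to -31% |
| weekly | 1 | -9% to -11% | 0.88-1.08 | -3% to +9% |
| weekly | 1.5 | +19% to +33% | 0.81-0.92 | -14% to -18% |

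Actual power is then 64% to 83%. Rate ratios of 0.6 and 0.8 change the last column by at most 2 points. With no frailty, score 1 gives +7% to +25% when negative dispersion estimates are set to zero.

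**4. Attacks rather than visits.** If 20% to 40% of attacks bring a second visit in the same month (assumed), score 1 errs by about -14% to +1% when three-visit months go in the one-or-two box, and by +2% to +25% when they go in the weekly box. Even the direction is not fixed.

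**5. Sampling error for comparison.** Exact counts from 100 children would still give a planned n anywhere from -27% to +33% of the truth (5th to 95th percentile).

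**6. The planned tests.** Power by simulation with 50 versus 50 children and frailty variance 1:

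| Summary and test | 2 vs 4 per year | 3 vs 6 per year |
|---|---|---|
| Exact count, Mann-Whitney | 73% | 76% |
| Months with a visit, Mann-Whitney | 71% | 74% |
| Either scoring of the boxes, Mann-Whitney | 71-72% | 74-75% |
| Any/none in the year, chi-squared | 34% | 28% |
| Any/none in the year, Fisher | 27% | 20% |

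Any/none does badly because most children have at least one visit: 1 - 1/(1+rate) is 67% versus 80%, and 75% versus 86%.

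**7. Steroids.** No arithmetic applies. The month-12 TRACK item gives any/none oral use over the year. Nothing on the monthly form reliably gives courses by month in a child on inhaled steroids.

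**The case against.** The strongest reply is that little is lost for this study. The protocol never says the primary outcome is a count, and months with a visit, which the form already yields, costs about two points of power. The large loss comes from choosing any/none, which is a gap in section 11 rather than in the form. All of this stands.

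The sizing harm falls on a later trial with an assumed design. With score 1, every shift (-20% to +9%) lies inside the sampling range for exact counts. That limits the harm but does not remove it: the coding error is systematic, adds to the sampling error, and is avoidable.

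The assumptions can also be challenged. Score 1.5 is a poor choice, since the mean in the one-or-two box is only 1.13 to 1.25 under this model. At 1 visit per year, score 1 changes the planned n by only -4% to -8%. In the no-frailty case, leaving negative dispersion estimates untruncated gives -10% to +11%. The larger figures are therefore the outer end of the range.

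Finally, other records probably exist. Sections 6 and 7.1 record stopping of inhaled steroids, added medication and referral, none of which the monthly form asks about. The case report form is not reproduced in the documents, and adverse events go into it. It may be a partial source, but no available text names it as the source for visit counts or oral courses. Free-text dose and duration may sometimes reveal a short oral course, but not reliably when both routes are used in one month.

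**Conclusion.** The concern holds. As written, the form cannot give a reliable attack count, nor monthly oral courses in children on inhaled steroids, although the protocol names it as the record of visits and of oral steroid use with dosage. This follows from the wording of the items and needs no assumed rate.

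The size does rest on assumptions: 2 to 6 visits per child-year, frailty variance 1, and a later trial sized on yearly counts. On that basis the visit rate errs by -25% to +33% and the later trial's planned size by -31% to +9%. With the better scoring (1), the size error is -20% to +9%.

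The group comparisons in this study are not threatened, provided section 11 does not settle on any/none in the year. The form should be fixed because the loss is avoidable at almost no cost.

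**What to change.** - **Question 3:** replace the boxes with the number of unscheduled visits for wheeze this month and, for each, the date and place (GP, urgent care, emergency department, admission).
- **Question 4:** split it into 4a, oral corticosteroid (yes/no, number of courses, start dates, dose), and 4b, inhaled corticosteroid (yes/no, drug, dose).
- **Section 11:** state the summary measure for the primary outcome and a fixed analysis rule for merging visits close in time into one attack.
- **Months already collected:** use the number of months with a visit, which needs no scoring. Ask for counts and dates at the three-monthly reviews and report them as recalled data. Check them against medical notes only if the consent described in section 13.5 covers that use. If a rate is still taken from banded months, report it under both scorings.

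The cost is two items on an electronic form, a few sentences in section 11 and a minor amendment. Parents spend about one extra minute in months with a visit or a steroid course. Back-filled months carry recall error. No extra patients or visits are needed.
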